Another approach to obtaining a sample from the lower airways is bronchoalveolar lavage (BAL). In this procedure, a fiberoptic bronchoscope is introduced into a segmental or subsegmental bronchus until the airway is occluded proximally, and saline solution is instilled and subsequently aspirated. The fluid recovered can then be submitted for cytological and microbiological analysis. BAL is used as a diagnostic and research tool in adults with lung problems and in children and infants with underlying respiratory diseases [de Blic, 2000]. It is regarded as the best technique for microbacteriological surveillance of young children with cystic fibrosis, providing more reliable information than sampling of the upper airway with oropharyngeal/ nasopharyngeal swabs or nasal lavage [Brennan, 2008]. The main limitation of this procedure is in its invasive nature. As contamination from the upper respiratory tract flora during the procedure can sometimes occur, its capacity to describe LRTI aetiology may be challenged. Hence, a suitable cut-off should be used to avoid making spurious conclusions [Woodhead, 2005].

Recent studies reporting results from bacterial culture of BAL fluid in children with respiratory symptoms have highlighted the importance of *H. influenzae*, *S. pneumoniae*, and *Moraxella catarrhalis* in chronic or recurrent presentations of the disease (Table 1).

Table 1 Bacterial aetiology of BAL fluid culture from children with respiratory symptoms (Amended 05 October 2015)

Reference	Population	Number of samples	H. influenzae	S. pneumoniae	M. catarrhalis
[De Schutter, 2011]	Acute nonresponsive CAP (cut off $\geq 10^4$ CFU/mL)	127	26%	6.3%	8.7%
	Recurrent CAP (cut off $\geq 10^4$ CFU/mL)	123	51.2%	7.3%	21.1%
[Hare, 2010]	Bronchiectasis (cut off $> 10^4$ CFU/mL)	45	47%	18%	20%
[Marchant, 2006]	Chronic cough of > 3 weeks duration of unknown etiology	20	47%	35%	26%
[Saito, 2006]	Persistent bacterial bronchitis (persistent, wet cough for > 1 month that resolves with appropriate antibiotic treatment)	19	26.3%	21%	42.1%
[Le Bourgeois, 2002]	Severe recurrent wheezy bronchitis unresponsive to inhaled steroids	30	30%	13.33%	10%
[Marguet, 1999]	5 groups:	72 (total)			
	asthma	12	8.33%	8.33%	16.67%
	chronic cough	9	33.33%	22.22%	11.11%
	infantile wheeze	23	30.43%	0.04%	13.04%
	cystic fibrosis	10	20%	10%	-
control	10	30%	-	-	
[Schellhase, 1998]	Recurrent wheezing	27	3.7%	-	7.4%

CAP = community-acquired pneumonia

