2. STUDY DESIGN

- Type of design: Epidemiological, interventional, multi-centre, hospital-based, cross-sectional study with prospective subject recruitment in Spain.
- Study population: Subjects aged ≥ 6 months to < 6 years visiting the study hospital with suspected chronic LRTI and for whom a BAL sample will be collected as per the recommendation of the clinician.

The following sub-group names will be used for the statistical analyses:

Identifier	Sub-group order in tables	Sub-group label in tables	Sub-group definition for footnote
Age	1	6-11M	6-11 months old subjects
	2	12-23M	12-23 months old subjects
	3	24-35M	24-35 months old subjects
	4	36-47M	36-47 months old subjects
	5	48-59M	48-59 months old subjects
	6	60-71M	60-71 months old subjects
Age2*	1	6-23M	6-23 months old subjects
	2	24-47M	24-47 months old subjects
	3	48-71M	48-71 months old subjects
Gender	1	F	Female
	2	M	Male
Pneumococcal vaccination history	1	Yes	Subjects received at least two doses or only one dose after one year of age of pneumococcal vaccination
	2	No	Subjects did not receive any dose or received only one dose within the first year of life of pneumococcal vaccination
	3	Unknown	History of pneumococcal vaccination is unknown
S. pneumoniae	1	S. pneumoniae +	Episode with S. pneumoniae positive by culture

Statistical Analysis Plan

Study alias & e-track number(s): EPI-STREP-064 BOD ES (115813)

status	2	S. pneumoniae -	Episode with S. pneumoniae negative by culture
H. influenzae status	1	H. influenzae +	Episode with H. influenzae positive by culture
	2	H. influenzae -	Episode with H. influenzae negative by culture
M. catarrhalis status	1	M. catarrhalis +	Episode with M. catarrhalis positive by culture
	2	M. catarrhalis -	Episode with M. catarrhalis negative by culture

* The age will be grouped into the following classes 6-11, 12-23, 24-35, 36-47, 48-59 and 60-71 months; however, if there are too few subjects in any of the categories, the classification of age2 will be used instead for subgroup analysis by age.

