4. ENDPOINTS

4.1. Primary endpoint

- 1) Occurrence of *H. influenzae*, *S. pneumoniae*, *M. catarrhalis* and other bacteria in BAL fluid samples of subjects aged ≥ 6 months to < 6 years visiting the hospital with suspected chronic LRTIs and an indication for BAL
 - *H. influenzae*, *S. pneumoniae* and *M. catarrhalis* confirmed by bacterial load $>10^4$ cfu/mL if present alone or 10^5 cfu/mL if present as co-infection.

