6.2. Analysis of primary objective

The primary analysis will be based on the ATP cohort. If the percentage of subjects from the Total effective cohort with serological results excluded from the ATP cohort is more than 5%, a second analysis based on the Total effective cohort will be performed to support the ATP analysis.

The proportions and associated exact 2-sided 95% confidence intervals (CI) of *H. influenzae*, *S. pneumoniae*, *M. catarrhalis* and other bacteria confirmed by culture in BAL samples (*H. influenzae*, *S. pneumoniae* and *M. catarrhalis* confirmed by bacterial load >10⁴ cfu/mL if present alone or 10⁵ cfu/mL if present as co-infection) will be computed and presented for all study subjects.

The denominators will be the number of tested subjects with BAL sample results available.

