Trimethoprim / sulfamethoxazole	$\leq 0.5/9.5$	1/19 – 2/38	$\geq 4/76$

The ranges for antimicrobial susceptibility for *H. influenzae* and *M. catarrhalis* are the following:

Table 3 MIC ranges for antimicrobial susceptibility for *H. influenzae* and *M. catarrhalis*

	Susceptible (S) ($\mu\text{g/mL}$)	Intermediate (I) ($\mu\text{g/mL}$)	Resistant (R) ($\mu\text{g/mL}$)
Penicilin	No CLSI standard – MIC values will be presented		
Amoxicillin / clavulanate	$\leq 4/2$	n.a.	$\geq 8/4$
Beta-lactamase (Nitrocefin)	Positive/Negative		
Erythromycin	No CLSI standard – MIC values will be presented		
Azithromycin	≤ 4	Non-susceptible (NS)	
Tetracycline	≤ 2	4	≥ 8
Levofloxacin	≤ 2	Non-susceptible (NS)	
Trimethoprim / sulfamethoxazole	$\leq 0.5/9.5$	1/19 – 2/38	$\geq 4/76$

8) To describe, according to microbiological results observed:

- Age, gender, weight, height and BMI categories
- Clinical symptoms and radiological evidence
- Pneumococcal conjugate vaccine, *H. influenzae* type b vaccine and influenza vaccine status
- Medical history and co-morbidities

Study alias & e-track number(s): EPI-STREP-064 BOD ES (115813)

- Information on feeding and day care practice, environmental exposure and smoking environment
- History of antibiotic use in the past six months as well as other treatments for chronic lower respiratory disease
- Laboratory results [including white blood cell counts, C-Reactive Protein (CRP) level and erythrocyte sedimentation rate, if available].

The demography characteristics (age, gender, weight in kg, height in cm and BMI categories), clinical symptoms and radiological evidence, Pneumococcal conjugate vaccine history status, *H. influenzae* type b vaccine history status and influenza vaccine history status, Medical history, Information on feeding and day care practice, environmental exposure and smoking environment, History of antibiotic use in the past six months as well as other treatments for chronic lower respiratory disease and Laboratory results will be presented by microbiological results of (*S. pneumoniae* positive/negative, *H. influenzae* positive/negative and *M. catarrhalis* positive/negative, co-infection or not co-infection), and by type of sample used (BAL or nasopharyngeal sample) (Details see section 6.1).

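### Pathogen status for the clinical profiles carries no bacterial-load rule and co-infection is undefined, so the BAL groups in SAP 6.3 item 8 need not match the primary-endpoint cases

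*SAP*

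**What the plan says.** SAP section 2 introduces its sub-group table with "The following sub-group names will be used for the statistical analyses". For each of *H. influenzae*, *S. pneumoniae* and *M. catarrhalis* the table gives two levels. The positive level for the pneumococcus reads "Episode with S. pneumoniae positive by culture", and the other entries follow the same pattern. No bacterial load and no sample type are given.

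SAP 6.3 item 8 (objective 9 in SAP 3.2) presents demography, symptoms, radiology, vaccination, antibiotic history and laboratory results by those positive/negative groups, and further as "co-infection or not co-infection), and by type of sample used (BAL or nasopharyngeal sample". Co-infection has no entry in the section 2 table.

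The primary endpoint in SAP 4.1 sets the load needed to confirm one of the three organisms in BAL: above 10^4 "cfu/mL if present alone or 10^5 cfu/mL if present as co-infection". SAP 6.2 writes the rule out again for the primary analysis ("if present as co-infection) will be computed and presented for all study subjects"), and 6.3 item 5 does so for nasopharyngeal occurrence. Item 8 does not.

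Protocol 1.1 explains why a load matters. BAL can be contaminated by upper-airway flora: "Hence, a suitable cut-off should be used to avoid making spurious conclusions".

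**The concern.** A programmer who follows the only written definition will put any child with growth in BAL, at any load, into the positive column. The item 8 tables would then profile a wider group than the primary table counts. The column totals would not match the primary numerators, and the added children are those whose growth the protocol regards as possibly contamination. If they resemble culture-negative children, the positive and negative profiles are drawn together.

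The co-infection split has a separate problem. With two levels and no definition, the second level is simply everyone else. A difference between the columns could then reflect two organisms against one, or infection against no infection, and the table could not tell them apart.

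**Working it through.** **The plan's own figure.** The documents' only sample-size figures are the exact 95% intervals in protocol 7.2 for 150 subjects. Clopper-Pearson limits give 17/150 = 11.3% (6.74; 17.52) and 50/150 = 33.3% (25.86; 41.48), which match the stated 6.7; 17.5 and 25.9; 41.5. These are not in dispute.

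**Setting the rules side by side.** Three BAL results under SAP 4.1 and under SAP section 2 as written:

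| BAL culture result | Primary endpoint (4.1) | Item 8 status (section 2) |
|---|---|---|
| One organism, 10^2 cfu/mL | not confirmed | positive |
| Two organisms, each 5×10^4 cfu/mL | neither confirmed | positive for both |
| One organism, 10^6 cfu/mL | confirmed | positive |

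Every confirmed case is culture-positive, so the primary cases are a subset of the positive group. The reverse does not hold.

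**Dilution (illustration).** The documents do not give the share *f* of culture-positives below the cut-off. Assume 50 of 150 children meet the 4.1 rule for one organism (the protocol's 33.3% example), a characteristic is present in 70% of them and 40% of all others, and children below the cut-off resemble negatives. Then the positive group has 50/(1 − *f*) children, and the apparent contrast is (1 − *f*)×70 + *f*×40 − 40 = 30×(1 − *f*) points.

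| *f* | Positive group | Of whom below the rule | Apparent contrast |
|---|---|---|---|
| 0 | 50 | 0 | 30 |
| 10% | 55.6 | 5.6 | 27 |
| 20% | 62.5 | 12.5 | 24 |
| 30% | 71.4 | 21.4 | 21 |
| 50% | 100 | 50 | 15 |

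**Make-up of the not co-infected column (illustration).** The rates are from protocol Table 1, for *H. influenzae*, *S. pneumoniae* and *M. catarrhalis* in that order. The organisms are assumed independent. P(none) is the product of (1 − p) over the three. P(one) is the sum of the three single-organism terms. The share with none is P(none)/[P(none) + P(one)].

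- Acute non-responsive pneumonia (26%, 6.3%, 8.7%): P(none) = 0.74×0.937×0.913 = 0.633. Of 150 children, about 95.0 have none, 48.8 one and 6.2 two or more. Share 95.0/143.8 = 66%.
- Recurrent pneumonia (51.2%, 7.3%, 21.1%): P(none) = 0.488×0.927×0.789 = 0.357. About 53.5, 74.7 and 21.8. Share 53.5/128.2 = 42%.
- Bronchiectasis (47%, 18%, 20%): P(none) = 0.53×0.82×0.80 = 0.348. About 52.2, 70.7 and 27.1. Share 52.2/122.9 = 42%.

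These three sets of rates were measured at a cut-off of about 10^4 cfu/mL. Counting any growth would lower the share with none.

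**The case against.** The section 2 entries are footnote labels, and silence on load is not a statement that any load counts. They could be shorthand for culture confirmation with the load rule attached. This is possible, but where the SAP wants the load rule it writes it out (4.1, 6.2, 6.3 item 5), and neither section 2 nor item 8 does so.

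The objective is to describe children by the microbiological results observed, and it names no threshold, so a grouping by any growth is permitted. That stands. The contamination remark in the protocol is background on BAL as a measure of aetiology and does not bind every secondary table. It does show why a reader would want to know which rule was used.

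Not co-infected could mean one organism only, since 4.1 contrasts an organism alone with co-infection. The SAP's abbreviation list mentions an annexed table template, which is not among the documents and might settle this. The pooling is therefore the literal reading, not an established fact. Item 8 also shows each organism separately, so infection against no infection for a given organism does not depend on this split.

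A reader might go further and infer that the profiles fail to describe the infections the primary endpoint counts, or that dilution is demonstrated. The documents support neither. All confirmed cases sit inside the positive groups. Dilution needs an unknown share below the cut-off and an assumption that those children resemble negatives; if some are truly infected, moving them to the negative column would blur the contrast from the other side. Item 8 specifies no test or between-group estimate. SAP 7.2 lists an interval for a difference in proportions but assigns it to no table.

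**Conclusion.** The point holds in a limited form. As written, item 8 groups BAL results by a rule different from that of the primary endpoint, and its co-infection split is undefined. Group sizes and profiles need not agree with the primary table. The primary estimate is untouched, because SAP 6.2 carries its own load rule.

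The size cannot be fixed from the documents. The fall from 30 points to between 27 and 15 rests on an assumed 10% to 50% of culture-positives below the cut-off and on their resembling negatives. The 42% to 66% of not co-infected children with no named organism rests on Table 1 rates, independence and the literal two-level reading. This is a cheap improvement to a descriptive secondary objective.

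**What to change.** In SAP section 2 and 6.3 item 8:

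- **BAL status.** Show three columns per organism: confirmed by the 4.1 rule, growth below that rule, and no growth. Growth below the rule should not be folded into the negatives.
- **Co-infection.** Replace the two-level split by none, one, and two or more of the three named organisms, counted by the 4.1 rule. Give the count by any growth as a labelled supplementary table. Two organisms at 5×10^4 each then fall under none confirmed in the main table and under two or more in the supplement. State whether other bacteria count. Because the 4.1 rule itself turns on co-infection, also state whether a second organism below its cut-off makes the first co-infecting.
- **Nasopharyngeal groups.** SAP 4.2 endpoint 5 speaks of detection by culture, while 6.3 item 5 applies the load rule. Reconcile these first, then use the same definition in item 8.

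The cost is SAP wording, table shells and slightly more table work. Quantitative culture of the three organisms in BAL is already planned (protocol Table 5), and the analysis runs once, after data cleaning. The downside is small positive columns. At the Table 1 pneumonia rates, 150×6.3% = 9.45 and 150×7.3% = 10.95, so about 9 to 11 children would be confirmed for *S. pneumoniae*.

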7. STATISTICAL CALCULATIONS

7.1. Derived and transformed data

Age at time of enrolment in the study will be computed as the difference between the date of enrolment [date when the ICF was signed by the parent(s)/ LAR(s)] and the date of birth. The age will be expressed in months.

The age will be grouped into the following classes 6-11, 12-23, 24-35, 36-47, 48-59 and 60-71 months; and also another category of 6-23, 24-47, 48-71 months just in case there will be too few subjects in the younger groups of 6-11 or 12-23 months.

BMI will be classified as below:

- Marked thinness: $<z$ -score (-3)
- Thinness: $\geq z$ -score (-3) and $< z$ -score (-2)
- Normal: $\geq z$ -score (-2) and $\leq z$ -score (1)
- Overweight: $> z$ -score (1) and $\leq z$ -score (2)
- Obesity: $> z$ -score (2) and $\leq z$ -score (3)
- Extreme obesity: $> z$ -score (3)

Statistical Analysis Plan

Study alias & e-track number(s): EPI-STREP-064 BOD ES (115813)

The source for the z-scores for age from 0 to 60 months is available on the WHO website BMI-for-age tables Girls z-scores

http://www.who.int/childgrowth/standards/b_f_a_tables_z_girls/en/

BMI-for-age tables Boys z-scores

http://www.who.int/childgrowth/standards/b_f_a_tables_z_boys/en/

The source for the z-scores for age from 61 months to < 6 years old is available on the WHO website of http://www.who.int/growthref/who2007_bmi_for_age/en/, enter the website, go to Tables, then z-scores: girls; and z-scores:boys (see for more details)

The pneumococcal conjugate vaccination status will be defined as:

- Vaccinated, if the subject either received at least two doses or received only one dose after one year of age;
- Unvaccinated, if the subject did not receive any dose or received only one dose within the first year of life;
- Unknown otherwise.

Temperature will be converted to axillary route temperature (if route is rectal or tympanic rectal, then value will be 0.5°C). If this derived value of temperature is $\geq 37.5^{\circ}\text{C}$, then the subject is considered to have fever.

7.2. Methods for CIs calculation

- The exact 95% CIs for a proportion within a group will be calculated from Proc StatXact [Clopper, 1934].
- Proc StatXact will be used to derive the standardised asymptotic 95% CI for the group difference in proportions [Robert G, 1998, method six]. The standardised asymptotic method used within GSK Biologicals is the method six.

8. CONDUCT OF ANALYSES

8.1. Sequence of analyses

The analyses will be performed in one step, when all data, will be available and cleaned. These analyses and associated individual data will be presented in a final study report.

Description	Analysis ID (SDD & CARS sub-folder)
Final	ANALYSIS_E1_01

8.2. Statistical considerations for interim analyses

No interim analysis is planned for this study.

9. CHANGES FROM PLANNED ANALYSES

N.A

11. APPENDIX

These pdf files for BMI categories for age by gender will be stored in the same location as SAP in eTMF

- BMI_boys_0_13_zscores.pdf
- BMI_boys_0_2_zscores.pdf
- BMI_boys_2_5_zscores.pdf
- BMI_girls_0_13_zscores.pdf
- BMI_girls_0_2_zscores.pdf
- BMI_girls_2_5_zscores.pdf
- BMifa_boys_5_19years_z.pdf
- BMifa_girls_5_19years_z.pdf
